11.2 Sample Size Considerations

We estimate, based on published results and our own experience, that 65% of all neonates born with vein of Galen malformation require urgent neonatal intervention (i.e. are NAR), under current standard of care. Thus, in order to achieve a cohort size of 20 treated patients, we expect to consent and screen 28-30 fetal patients. We expect to enroll 25 participants to account for withdrawals prior to completing the intervention (due to failure to achieve near ideal fetal position or other reasons). The study will be closed to enrollment once 20 participants have completed the intervention. Using the prescreening technique we have developed based on fetal MRI measurement of straight sinus or falcine sinus caliber at the narrowest point, we can estimate that 80% of all such fetal VOGM patients will progress to NAR status without fetal intervention. Setting a goal of reducing this fraction to 30% NAR status after fetal intervention (i.e., a 50% absolute reduction), the proposed sample size will provide 80% power to detect a significant effect of fetal intervention.

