11.3 Safety Review

Two-stage design for safety endpoint

In Stage 1, up to 11 evaluable patients will be enrolled (**Table 2**). Out of 11 patients, if 3 or more patients experience an unacceptable event (see definition in Section 3.2 above and recapitulated below Table 2), the intervention is unsafe and not worthy of further study. If 2 or fewer experience any unacceptable event, the trial will proceed to Stage 2, where an additional 9 evaluable patients will be enrolled, for a total of $N=20$ evaluable patients. Out of $N=20$ patients, if 4 or more patients experience any unacceptable event, the intervention is unsafe and not worthy of further study. If 3 or fewer patients experience any unacceptable event, the intervention is sufficiently safe and worthy of further study. In addition, in case of a single maternal death, the study will be halted pending review by the DSMB and the FDA.

This design tests the null hypothesis that the rate of unacceptable events is $P > 30\%$ versus the alternative that $P < 5\%$. The total type I error rate is 0.097 and the power is 97.5%. If the intervention is truly unsafe, there is a 68.7% probability of early trial termination.

Table 2: Decision rules for safety based on the optimum two-stage design.

	Cumulative number of patients with unacceptable events	Decision
Stage 1: Enroll 11 patients	3 or more	Terminate the trial: agent not worthy of further study
	2 or fewer	Inconclusive result: proceed to Stage 2
Stage 2: Enroll 9 additional patients	4 or more	Terminate the trial: agent not worthy of further study
	3 or fewer	Trial concludes: agent worthy of further study

- 1) Unacceptable events within 7 days of fetal embolization include:
 - a) Fetal death
 - b) Fetal intracranial hemorrhage, either parenchymal or extra-axial, other than petechial hemorrhage. A petechial hemorrhage is seen as focal staining of the brain parenchyma by blood products on MRI, is not associated with mass effect, and there are minimal neurologic sequelae. Petechial hemorrhages are usually considered non-serious adverse events in trials.
 - c) Maternal death
- 2) Unacceptable events occur between fetal embolization and delivery include:
 - a) Intra-procedural and post-procedural morbidity to the fetus and mother, probably related to the fetal intervention, e.g. placental abruption with subsequent sequelae
 - b) Preterm delivery < 28 weeks, probably related to the fetal intervention

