11.4 Efficacy Review

Two-stage design for efficacy endpoint

In Stage 1, up to 11 evaluable patients will be enrolled (**Table 3**). Out of 11 patients, if 5 or fewer patients respond, i.e. do not experience a serious postnatal event (see definition in Section 3.2 above), the intervention is not efficacious and not worthy of further study. If 6 or more respond, the trial will proceed to Stage 2, where an additional 9 evaluable patients will be enrolled, for a total of N=20 evaluable patients. Out of N=20 patients, if 10 or fewer patients respond, the intervention is not sufficiently efficacious and not worthy of further study. If 11 or more patients respond, the intervention is sufficiently efficacious and worthy of further study.

This design tests the null hypothesis that the response rate is $P \leq 40\%$ versus the alternative that $P \geq 70\%$. The total type I error rate is 0.099 and the power is 90.2%. If the intervention is truly not efficacious, there is a 75.3% probability of early trial termination.

Table 3: Decision rules for efficacy based on the optimum two-stage design.

	Cumulative number of responses	Cumulative number of non-responders (patients with serious postnatal events)	Decision
Stage 1: Enroll 11 patients	5 or fewer	6 or more	Terminate the trial: fetal intervention not worthy of further study
	6 or more	5 or fewer	Inconclusive result: proceed to Stage 2
Stage 2: Enroll 9 additional patients	10 or fewer	10 or more	Terminate the trial: fetal intervention not worthy of further study
	11 or more	9 or fewer	Trial concludes: fetal intervention worthy of further study

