11.5 Timing of safety and efficacy rules

The safety endpoint is observed from Day 0 (the day of fetal intervention) to Day 7 post-intervention. The efficacy endpoint is observed from the birth to Day 30 of life. Both safety and efficacy decision rules must be satisfied before enrollment to Stage 2 is allowed. Prior to initiating accrual at Stage 2, a sensitivity analysis will be performed to determine if both the safety and efficacy rules would be triggered. Hence, trial enrollment for Stage 2 may be suspended after the enrollment of the 11th patient to allow observation up to Day 30 of life of the most recently treated patient.

The safety and efficacy rules are to be interpreted as specifying that the trial will stop as soon as either criterion is reached; e.g., if the first 3 evaluable patients experience unacceptable prenatal events (safety rule), or the first 6 patients experience serious postnatal events (efficacy rule), then the trial stops immediately. Beyond the 11th patient, the trial halts as soon as 4 unacceptable prenatal events or 10 serious postnatal events occur.

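### The stated powers of 97.5% (safety) and 90.2% (efficacy) hold for each rule run alone; with both rules active the chance of reaching the safe conclusion at 5% events and 70% response is about 88%

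*Combined protocol and SAP*

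**What the plan says.** Section 11.3 sets the primary safety rule. Stage 1 fails on this condition: "Out of 11 patients, if 3 or more patients experience an unacceptable event". At 20 patients, "if 4 or more patients experience any unacceptable event, the intervention is unsafe and not worthy of further study"; with 3 or fewer, the procedure is declared sufficiently safe. The hypotheses are an event rate above 30% against one below 5%. The section reports: "The total type I error rate is 0.097 and the power is 97.5" per cent.

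Section 11.4 sets the secondary efficacy rule on the same 11 + 9 patients. The trial needs at least 6 responders of 11 to continue and at least 11 of 20 to succeed, for a null response rate of 40% or less against 70% or more. The section reports: "The total type I error rate is 0.099 and the power is 90.2" per cent.

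Section 11.5 joins the two. Both rules must be satisfied before Stage 2 opens, and "the trial will stop as soon as either criterion is reached". After the 11th patient the trial halts at 4 safety events or 10 patients with serious postnatal events. The documents give no joint operating characteristics. The sensitivity analysis planned before Stage 2 only checks whether the rules would be triggered.

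**The concern.** The safety rule can return a favourable answer only at 20 patients (Table 2), and the efficacy rule can end the trial before then. If it does, the plan defines no safety conclusion, however few unacceptable events have occurred. The 97.5% in Section 11.3 therefore does not give the probability that a safe procedure is declared safe in the trial as Section 11.5 runs it. Safety is the primary objective, so the shortfall falls on the main question of the study. It grows as the response rate drops, and a safe but weakly effective procedure is a realistic outcome for a first-in-fetus intervention.

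**Working it through.** **Inputs.** Safety (11.3): 11 then 9 patients; continue with at most 2 events of 11; safe with at most 3 of 20; rates 30% and 5%. Efficacy (11.4): continue with at least 6 responders of 11; success with at least 11 of 20; rates 40% and 70%. Joint operation: 11.5. The dependence between a safety event and non-response is not given, so three cases are used: never in the same patient (disjoint), independent, and every safety event also a non-response (nested).

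**Step 1: reproduce the plan's figures, each rule alone.** With b(n, x, p) the binomial probability:

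P(safe) = sum over x = 0 to 2 of b(11, x, p) × P(at most 3 − x events in 9).

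- p = 0.05: 0.5688 × 0.9994 + 0.3293 × 0.9916 + 0.0867 × 0.9288 = 0.9755. The plan states 97.5%.
- p = 0.30: 0.0198 × 0.7297 + 0.0932 × 0.4628 + 0.1998 × 0.1960 = 0.0967. The plan states 0.097.
- Stage 1 stop at p = 0.30: 0.6873. The plan states 68.7%.

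P(efficacious) = sum over x = 6 to 11 of b(11, x, r) × P(at least 11 − x responders in 9).

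- r = 0.70: 0.1190 + 0.2146 + 0.2557 + 0.1997 + 0.0932 + 0.0198 = 0.9020. The plan states 90.2%.
- r = 0.40: 0.0990. The plan states 0.099.
- Stage 1 stop at r = 0.40: 0.7535. The plan states 75.3%.

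Every stated figure is right for a rule run alone.

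**Step 2: both rules active.** The trial reaches a safe conclusion at 20 patients only if events stay at or below 2 through patient 11 and 3 through patient 20, and non-responders at or below 5 and then 9. If the endpoints are independent, the probability is the product: 0.9755 × 0.9020 = 0.8798. An exact patient-by-patient recursion gives 0.8782 if disjoint and 0.8864 if nested. Dependence hardly matters.

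**Step 3: vary the true rates (independent case, product of the two single-rule values).**

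| True response | Efficacy rule alone | Both rules, 5% events | Both rules, 10% events |
|---|---|---|---|
| 40% | 0.099 | 9.7% | 8.3% |
| 50% | 0.339 | 33.0% | 28.4% |
| 60% | 0.666 | 65.0% | 55.9% |
| 65% | 0.804 | 78.4% | 67.5% |
| 70% | 0.902 | 88.0% | 75.7% |
| 75% | 0.960 | 93.6% | 80.6% |
| 80% | 0.987 | 96.3% | 82.9% |
| 90% | 1.000 | 97.5% | 83.9% |

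The safety rule alone gives 0.9755 at 5% events and 0.8395 at 10%.

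**Step 4: softer readings of the efficacy stop (5% events).**

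| Reading | 70% response | 40% response |
|---|---|---|
| Efficacy stop at any patient blocks the safety conclusion | 87.8–88.6% | 9.2–9.9% |
| A stop triggered only by the 20th patient does not block it | 88.8–89.5% | 12.6–13.4% |
| As above, with two further outcomes pending when the 20th is treated (assumed; independent) | 89.8% | 20.4% |
| Efficacy acts only at the Stage 1 gate | 89.8–90.5% | 23.3–24.4% |

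**Step 5: false-safe error.** At 30% events and 70% response, independent: 0.0967 × 0.9020 = 0.0872, against 0.0967 alone.

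**The case against.** The strongest reply is that nothing stated is miscalculated. Each power appears under the heading of its own rule and beside its own hypotheses, so a careful reader can see that it belongs to one rule. That is fair as to the arithmetic. It does not supply the missing figure: Section 11.5 changes the trial to which the powers apply, and no joint value is given.

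A second reply is that stopping at low response is intended. Section 11.4 already reports a 75.3% chance of early termination at the null response rate, and halting exposure to an ineffective fetal procedure is the purpose of the rule. This stands. The low values at 40% response are the futility rule doing its work and are no reason to change it. What is missing is a statement of what happens to the primary safety conclusion when that rule fires.

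A third reply is that efficacy is known only at day 30 of life, so outcomes lag behind treatment. This also stands in part. With two further outcomes pending, the value at 40% response rises from 13% to about 20%, but at 70% it moves only from 88.9% to 89.8%.

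Two stronger readings are tempting and are not supported. A reader might infer that 88% to 89% is a ceiling. It is not: the alternatives are 70% response or more and fewer than 5% events, so 5%/70% is the least favourable corner of that region, and the joint figure rises with better response. At 70% response it also rises with fewer events, to about 90% at a 2% event rate. A reader might also tie the 90.2% to the target in Section 11.2, "Setting a goal of reducing this fraction to 30% NAR status after fetal intervention", and call it an upper limit for that target. Section 11.2 attaches 80% power to that goal, and Section 11.4 does not link its composite response rate to it.

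**Conclusion.** The point holds as an omission that affects the stated power of the primary endpoint. At a 5% event rate and 70% response, the trial as run has about an 88% chance of reaching the safe conclusion, or about 89% if an efficacy stop at the 20th patient does not block it. The chance of missing that conclusion for a procedure with a 5% event rate is therefore about 11% to 12%, where the plan's figure implies 2.5%. The gap almost closes if response is 80% or more and widens quickly below 70%.

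The result assumes that an efficacy stop before 20 patients prevents the favourable safety conclusion. Section 11.5 and Table 2 support this, though neither says it outright. The low-response values also assume that efficacy outcomes are known at once; a lag raises them. Even if efficacy acted only at the Stage 1 gate, contrary to Section 11.5, the figure at 5%/70% would be about 90%. Error control is not harmed: the false-safe error falls slightly, to 0.087 at 70% response if the endpoints are independent.

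**What to change.** In Sections 11.3 and 11.4, label 97.5% and 90.2% as the power of each rule run alone. In Section 11.5, add the joint figure of about 88% at 5% events and 70% response, with a short table over event and response rates such as the one in Step 3, and state the dependence and timing assumptions. Also in Section 11.5, state that if the efficacy rule stops the trial, the safety result is still reported as an event rate with an exact confidence interval on all treated subjects.

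The cost is a few sentences and one table. The stated power becomes less favourable. No extra patients are needed, and neither the decision boundaries nor the stopping rules change.

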12 SOURCE DOCUMENTS AND ACCESS TO SOURCE DATA/DOCUMENTS

Study staff will maintain appropriate medical and research records for this study, in compliance with ICH E6, Section 4.9 and regulatory and institutional requirements for the protection of confidentiality of subjects. Study staff will permit authorized representatives of regulatory agencies to examine (and when required by applicable law, to copy) research records for the purposes of quality assurance reviews, audits, and evaluation of the study safety, progress and data validity.

13 ETHICS/PROTECTION OF HUMAN SUBJECTS

13.1 Ethical Standard

The investigator will ensure that this study is conducted in full conformity with the principles set forth in The Belmont Report: Ethical Principles and Guidelines for the Protection of Human Subjects of Research, as drafted by the US National Commission for the Protection of Human Subjects of Biomedical and Behavioral Research (April 18, 1979) and codified in 45 CFR Part 46 and/or the ICH E6.

13.2 Institutional Review Board

The protocol, informed consent form(s), recruitment materials, and all subject materials will be submitted to the IRB for review and approval. Approval of both the protocol and the consent form must be obtained before any subject is enrolled. Any amendment to the protocol will require review and approval by the IRB before the changes are implemented in the study.

13.3 Informed Consent Process

Both parents of fetuses who meet all entry criteria for fetal intervention and who wish to continue in the enrollment process will undergo a formal Informed Consent discussion and will both be required to sign the consent form in order to participate in the study.

The father's consent need not be obtained if he is unable to consent because of unavailability, incompetence, or temporary incapacity, or if the pregnancy resulted from rape or incest.

Informed consent is a process that is initiated prior to the individual agreeing to participate in the study and continues throughout study participation. Extensive discussion of risks and possible benefits of study participation will be provided to subjects and their families, if applicable. A consent form describing in detail the study procedures and risks will be given to the subject. Consent forms will be IRB-approved, and the subject is required to read and review the document or have the document read to him or her. The investigator or designee will explain the research study to the subject and answer any questions that may arise. The subject will sign the informed consent document prior to any study-related assessments or procedures. Subjects will be given the opportunity to discuss the study with their surrogates or think about it prior to agreeing to participate. They may withdraw consent at any time throughout the course of the study. A copy of the signed informed consent document will be given to subjects for their records. The rights and welfare of the subjects will be protected by emphasizing to them that the quality of their clinical care will not be adversely affected if they decline to participate in this study.

The consent process will be documented in the clinical or research record.

13.4 Subject Confidentiality

Subject confidentiality is strictly held in trust by the investigators, study staff, and the sponsor(s) and their agents. The study protocol, documentation, data, and all other information generated will be held in strict confidence. No information concerning the study or the data will be released to any unauthorized third party without prior written approval of the sponsor.

The study monitor or other authorized representatives of the sponsor may inspect all study documents and records required to be maintained by the investigator, including but not limited to, medical records (office, clinic, or hospital) for the study subjects. The clinical study site will permit access to such records.

13.5 Future Use of Identifiable Data

Identifiable data from this study will be stored for future use and future research. Subjects will be informed of this in the informed consent form. Any data that is shared outside of the study will be labeled with a code. The key to the code will be kept on a password-protected computer.

14 DATA HANDLING AND RECORD KEEPING

The investigators are responsible for ensuring the accuracy, completeness, legibility, and timeliness of the data reported. All source documents should be completed in a neat, legible manner to ensure accurate interpretation of data. The investigators will maintain adequate case histories of study subjects, including accurate case report forms (CRFs), and source documentation.

14.1 Data Management Responsibilities

Data collection and accurate documentation are the responsibility of the study staff under the supervision of the investigator. All source documents and laboratory reports must be reviewed by the study team and data entry staff, who will ensure that they are accurate and complete. Unanticipated problems and adverse events must be reviewed by the investigator or designee.

14.2 Data Capture Methods

Data will be entered into REDCap Cloud, a 21 CFR 11 FDA-compliant electronic database.

14.3 Study Records Retention

Record retention: An investigator shall retain records required to be maintained for a period of 2 years after the latest of the following dates: (a) date on which clinical investigation is terminated; or (b) data is no longer required to support FDA pre-market approval application, or the FDA is notified of discontinuation of application.

IRB records: The records required by this policy shall be retained for at least 3 years, and records relating to research which is conducted shall be retained for at least 3 years after completion of the research. All records shall be accessible for inspection and copying by authorized representatives of the appropriate department or agency at reasonable times and in a reasonable manner.

APPENDIX A: SCHEDULE OF EVENTS

		Screening and Baseline (Visit 1)	Study Intervention (Visit 2)	Pre-delivery follow up visits (clinical care)	6 month visit (Visit 3) ± 1 month	12 month visit (Visit 4) ± 1 month	18 month visit (Visit 5) ± 1 month	24 month visit (Visit 6) ± 1 month
Procedures								
Signed Consent Form	X							
Assessment of Eligibility Criteria	X							
Review of Medical History	X							
Review of Concomitant Medications	X	X	X	X	X	X	X	
Study Intervention		X						
Fetal ultrasound, fetal echocardiogram, and fetal MRI	X		X					
Assessment of Adverse Events		X	X	X	X	X	X	
Neurological assessments	Vineland Adaptive Behavior Scales				X	X	X	X
	REEL				X	X	X	X
	CBCL						X	X
	Bayley Exam						X*	X*
	DAYC-2						X	X

*Only performed if visit is in person.
